6.2.3.2. Handling of Missing/Partial Dates

When missing/partial dates of concomitant medications are used to classify time windows, the following standard rules will be applied:

If only the day is missing:

- For the start date, the first day of the month (01) will be used.
- For the stop date, the last day of the month will be used.

If both day and month are missing:

- For the start date, the first day of the month (01) and July will be used if the year is prior to the year of study entry. If the year is the same as study entry, then the first day (01) of January will be used.
- For the stop date, the last day of the month (31) and July will be used if the year is prior to the year of study entry. If the year is the same as study entry, then the last day (31) of December will be used, unless this is after the patient completion/withdrawal date; in this case, the date of completion/withdrawal will be used.

If year is missing:

- For the start date, the year of study entry will be used.
- For the end date, the date of completion/withdrawal will be used.
- If the start date is completely missing, the date of study entry will be used.

If end date is completely missing, then the therapy will be assumed to be ‘Ongoing’; in this case, the date of completion/withdrawal will be used. The following rules apply for missing/partial start dates of unsolicited AE:

- Unsolicited AE start dates with missing day:
 - If the event starts in the same month as the date of vaccination (Day 1), the contents of AE.AESTTPT (the flag indicating if the event occurred before or after study dose) will be used to complete the date. If ‘after study dose’ is selected, the imputed start date will match the date of vaccination (Day 1). If ‘before study dose’ is selected, the imputed date will be one day before the date of vaccination (Day 1).
- Unsolicited AE start dates with missing day and month:
 - If the event starts in the same year as the date of vaccination (Day 1), the contents of AE.AESTTPT (the flag indicating if the event occurred before or after study dose) will be used to complete the date. If ‘after study dose’ is selected, the imputed start date will match the date of vaccination (Day 1). If ‘before study dose’ is selected, the imputed date will be one day before the date of vaccination (Day 1).
- Unsolicited AE start dates with missing day, month, and year:
 - The contents of AE.AESTTPT (the flag indicating if the event occurred before or after study dose) will be used to complete the date. If ‘after study dose’ is selected, the imputed start date will match the date of vaccination (Day 1). If ‘before study dose’ is selected, the imputed date will be one day before the date of vaccination (Day 1).

All other cases of incomplete unsolicited AE start date will follow the standard rules above.

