4.1.3. Baseline Definition

Unless otherwise specified, baseline will be defined as the last non-missing measurement taken prior to reference start date (including unscheduled assessments). In the case where the last non-missing measurement and the reference start date coincide, that measurement will be considered baseline. AEs and medications commencing on the reference start date will be considered post-baseline unless otherwise indicated based on available start date/time combination or collected Electronic Case Report Form (eCRF) information that identifies the individual event/medication as starting prior to first study vaccination administration.

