4.4.1.7. Other Safety Analyses Endpoints

For the analysis of vaccine safety, the following parameters and the 95% CI will be calculated:

- The percentage of participants with at least 1 administration-site AE (solicited and/or unsolicited), with at least 1 general AE (solicited and/or unsolicited) and with any AE (solicited and/or unsolicited) during the solicited follow-up period after vaccination will be tabulated with exact 95% CI on the ES.
- The percentage of participants reporting each individual solicited administration-site (any, Grade 3) and general (any, Grade 3 or 4, related, medically attended) AE during the solicited follow-up period after vaccination will be tabulated with exact 95% CI on the SSS.
- The duration statistics (in terms of number of days, See section 6.2.2) of each solicited administration-site and general AE during the Day 7 post-vaccination follow-up period will be tabulated on the SSS.
- The percentage of participants reporting ongoing solicited (administration-site and general) AEs at the end of the solicited follow-up period will be tabulated with exact 95% CI on the SSS.
- Temperature will be reported per 0.5°C cumulative increments beginning ($\geq 38, \geq 38.5, \geq 39, \geq 39.5, \geq 40$) during the solicited follow-up period for the SSS.
- The percentage of participants with at least 1 report of an unsolicited AE (any, Grade 3, related, Grade 3 related, medically attended) classified by the MedDRA during the follow-up period will be tabulated with exact 95% CI on the SSS.
- The percentage of participants who started to receive at least 1 concomitant medication during the follow-up period will be tabulated with exact 95% CI for the ES.

- The percentage of participants with at least 1 report of SAE (any, related, fatal, fatal related) classified by MedDRA during the trial period will be tabulated with exact 95% CI for the ES.
- The percentage of participants with at least 1 report of a MAE (medically attended event) classified by MedDRA during the trial period will be tabulated with exact 95% CI for the ES.
- SAEs and withdrawals due to AE(s) will be described in detail in Listings for the ES.

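### SAP 6.2.3.2 dates partially recorded medications to the earliest possible day, so some drugs started after vaccination leave the planned count of participants who started a medication; the net direction is unknown

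*SAP*

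**What the plan says.** SAP 6.2.3.2 states the purpose of its rules: "When missing/partial dates of concomitant medications are used to classify time windows, the following standard rules will be applied". For start dates they are:

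- Day missing: "For the start date, the first day of the month (01) will be used".
- Day and month missing, entry year: "If the year is the same as study entry, then the first day (01) of January will be used".
- Day and month missing, earlier year: "the first day of the month (01) and July will be used if the year is prior to the year of study entry".
- Nothing known: "If the start date is completely missing, the date of study entry will be used".

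The output that depends on this is in SAP 4.4.1.7: "The percentage of participants who started to receive at least 1 concomitant medication during the follow-up period", with an exact 95% CI on the Exposed Set. Protocol 6.4.4 plans the same output. Under SAP 6.1.7 and Protocol 5.3.5, drugs already in use at enrollment and drugs started during the trial are recorded together. The start date relative to vaccination therefore decides who is counted. On the boundary, SAP 4.1.3 says "AEs and medications commencing on the reference start date will be considered post-baseline", unless a time or an eCRF item shows an earlier start.

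For unsolicited AEs, SAP 6.2.3.2 works differently. If the partial date falls in the vaccination month or year, or is wholly missing, a flag for before or after the dose decides. After gives the vaccination date, and before gives the preceding day. No such step is stated for medications.

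**The concern.** If only the month of a drug's start is known and it is the vaccination month, the rule dates the drug to the 1st. Unless vaccination was itself on the 1st, the drug then counts as started before vaccination, whatever the truth. If only the year is known and it is the entry year, the drug is dated to 1 January with the same effect. For these records the error runs one way: a true post-vaccination start can be moved before Day 1, but no earlier start can be moved after it.

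At stake is one planned safety percentage and its confidence interval. Treatment started after vaccination is a rough marker of events that needed care, so records should not leave the count only because a day was not written down.

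**Working it through.** **Plan's own figures.** The documents give no expected rate of medication starts and no expected share of partial dates, so there is no stated figure on this point to reproduce. The exact 95% CI widths in SAP Table 2 for N = 250 (1.67, 3.00, 7.83 and 12.73 points at 0.1%, 1%, 10% and 50%) do reproduce, and serve as a yardstick below.

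**Assumptions.** The medication follow-up period is taken as Day 1-21, the period SAP 4.2.2 gives for unsolicited AEs. Vaccination day is uniform over the calendar month, and true start day is uniform over Day 1-21.

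**Share moved, only the day missing.** A start is moved before vaccination if it falls in the vaccination month and vaccination was not on the 1st. In a 30-day month there are 30 × 21 = 630 pairs of vaccination day and start day.

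- Vaccination on days 1-10: all 21 starts fall in the same month, 10 × 21 = 210.
- Vaccination on days 11-30: 20 + 19 + … + 1 = 210.
- Less the 21 pairs with vaccination on the 1st: 420 − 21 = 399.
- m = 399/630 = 63.3%.

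The same count gives 357/588 = 60.7% for a 28-day month and 420/651 = 64.5% for a 31-day month. The share depends strongly on the vaccination day. In a 30-day month it is 0% for the 1st, 100% for the 2nd to 10th, 76% for the 15th (16/21), 52% for the 20th (11/21), 29% for the 25th (6/21) and 5% for the 30th (1/21). Starts in the following month are dated to the 1st of that month, after vaccination, and stay counted.

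**Share moved, day and month missing, entry year.** All are moved, unless vaccination was on 1 January. No rule covers a start in the year after entry with day and month missing, which could arise after a December vaccination.

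**Effect on the percentage.** Let P be the true percentage of starters and f the share of starters whose only new drug has a partial date of the kind considered. Then reported percentage = P(1 − f·m), with m = 0.633 (day missing) or 1 (1 January). P and f are assumptions. Loss in percentage points, day missing / 1 January:

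| P | f = 2% | f = 5% | f = 10% | f = 20% |
|---|---|---|---|---|
| 10% | 0.13 / 0.20 | 0.32 / 0.50 | 0.63 / 1.00 | 1.27 / 2.00 |
| 30% | 0.38 / 0.60 | 0.95 / 1.50 | 1.90 / 3.00 | 3.80 / 6.00 |
| 50% | 0.63 / 1.00 | 1.58 / 2.50 | 3.17 / 5.00 | 6.33 / 10.00 |

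For example, 30% × (1 − 0.05 × 0.633) = 29.05%. At f = 5% the day-missing loss is 0.32 points against a CI width of 7.83 (P = 10%), and 1.58 against 12.73 (P = 50%).

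**Opposite effect.** A wholly missing start becomes study entry. Consent, enrollment and vaccination all fall on Day 1 in Protocol Table 2, so under SAP 4.1.3 the drug is post-baseline by default. Let g be the share of non-starters with an ongoing drug dated this way. It cancels the loss when (1 − P)·g = P·f·m. At P = 30% and f = 5%, g = 0.30 × 0.05 × 0.633 / 0.70 = 1.36%.

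**The case against.** The strongest objection concerns direction. A reader might infer that the percentage is biased low overall. The documents do not support that. The rule for wholly missing dates can turn a long-standing drug into a new start, and participants are aged 65 or older with their ongoing drugs recorded. Under the assumptions above, about 1.4% of non-starters with such a record would be enough to cancel the day-missing loss. The eCRF exception in SAP 4.1.3 may limit this upward effect, while no stated item corrects the downward one. The net sign still depends on a mix of missing dates that is not given. This objection stands.

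It also stands that the event may be rare. Concomitant medication is collected at Day 1, at the Day 8 call and at Day 22 (Protocol Table 6). Start and end dates must be recorded (Protocol 5.3.5), and programmed edits query missing data (Protocol 7.6). A start within the last three weeks whose month is unknown should be unusual, so the 1 January case may be nearly empty.

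Three further inferences go too far:

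- That every partially dated post-vaccination drug is lost. About a third of day-missing starts stay counted, and a participant leaves the numerator only if every new drug is affected.
- That AEs default to the vaccination date. They follow the before/after flag, and AE dates outside its scope fall back on these same standard rules. A blanket default to vaccination for medications would not match the AE rule and could count ongoing drugs as new.
- That separating an AE from its treatment distorts a planned result. The dates can separate, but no planned table identified here links the two.

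The objection does not remove the core. Two misclassifications of unknown size in opposite directions make the percentage harder to read, and the SAP already has a better method in the same section.

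**Conclusion.** The point holds for a defined group of records. For partial medication start dates in the vaccination month or entry year, SAP 6.2.3.2 moves true post-vaccination starts before Day 1: about 61% to 65% when only the day is missing, given uniform vaccination and start days, and essentially all under the 1 January rule. These starts leave the planned percentage unless the participant has another correctly dated new drug. For P of 10% to 50% and f of 2% to 20%, the loss is 0.1 to 6.3 points (day missing) or 0.2 to 10.0 points (1 January), before any offset from wholly missing dates. The upper ends need a large share of partial dates, for which the documents give no evidence.

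The net direction and real size are unknown. The output is a descriptive line among the other safety analyses and no hypothesis is tested, so the primary and secondary endpoints are untouched. This is a minor correction, worth making because it is cheap.

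**What to change.** Amend SAP 6.2.3.2 for medication start dates that are partial and compatible with the vaccination month or year, or are completely missing:

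- If the drug was recorded as in use at the Day 1 visit, or its stop date or another eCRF item shows use before vaccination, impute the day before vaccination.
- Otherwise, impute the vaccination date.
- Report the number of imputed start dates with the SAP 4.4.1.7 output.

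This follows the logic of the unsolicited-AE rule and addresses both errors: new drugs are no longer moved before Day 1, and drugs shown to be ongoing are no longer counted as new. The wording should also cover a start in the calendar year after entry with day and month missing.

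The cost is a few sentences in the SAP, provided the eCRF shows which drugs were in use at Day 1; the documents schedule that collection but do not describe the form. No endpoint, sample size or analysis set changes. The downside is that a few prior medications without any such information may count as new. The reported number of imputed dates lets a reader judge whether that matters.

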4.2. Primary Endpoint(s) Analyses

4.2.1. Definition of Endpoints

Number and percentage of subjects with solicited AEs (administration-site as well as systemic) for 7 days from the reference start date (Day 1).

Number and percentage of subjects with unsolicited AEs starting from reference start date for 21 days i.e. up to Day 21.

Number and percentage of subjects with SAEs from the reference start date for 21 days i.e. up to Day 21.

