4.2.2. Main Analytical Approach

The primary endpoint analyses related to solicited AEs will be performed on the SSS. The primary endpoint analyses related to unsolicited AEs will be performed on the ES.

The number and percentage of participants reporting solicited administration-site AE (any, Grade 3, medically attended), systemic AE (any, Grade 3 or Grade 4, medically attended) and either administration-site or systemic AE (any, Grade 3, medically attended) during the follow-up period (Day 1 – Day 7) will be tabulated with exact Clopper-Pearson 95% CI.

The number and percentage of participants reporting at least 1 unsolicited AE (any, Grade 3, related, Grade 3 related, medically attended) classified by the Medical Dictionary for Regulatory Activities (MedDRA) during the 21-day follow-up period (Day 1 - Day 21) will be tabulated with exact 95% CI, overall and by MedDRA System Organ Class (SOC) and Preferred Term (PT).

The number and percentage of participants reporting at least 1 SAE (any, fatal, related, fatal related) during the trial period (Day 1 - Day 21) will be tabulated with exact 95% CI, overall and by MedDRA SOC and PT.

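### An unsolicited AE start date lacking only the year takes the study-entry year and ignores the before/after-dose flag, so a January onset after a 12–31 December vaccination leaves the primary Day 1–21 count

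*SAP*

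**What the plan says.** SAP 6.2.3.2 opens with rules for medication: "When missing/partial dates of concomitant medications are used to classify time windows, the following standard rules will be applied". Among these, when the year of a start date is missing: "For the start date, the year of study entry will be used". When day and month are both missing, the start-date rule covers a year before study entry and a year equal to it, and no other.

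Rules for unsolicited AE start dates follow. The flag AE.AESTTPT, which records whether the event began before or after the study dose, decides in three patterns:

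- Day missing: "If the event starts in the same month as the date of vaccination (Day 1), the contents of AE.AESTTPT" is used.
- Day and month missing: "If the event starts in the same year as the date of vaccination (Day 1), the contents of AE.AESTTPT" is used.
- All parts missing ("Unsolicited AE start dates with missing day, month, and year"): the flag is used without further condition.

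In each, an event flagged as after the dose is dated to the vaccination date. Everything else falls to one sentence: "All other cases of incomplete unsolicited AE start date will follow the standard rules above".

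These dates feed a primary endpoint. SAP 4.2.1 defines it as "Number and percentage of subjects with unsolicited AEs starting from reference start date for 21 days i.e. up to Day 21", and SAP 4.2.2 has the any, Grade 3, related, Grade 3 related and medically attended counts "during the 21-day follow-up period (Day 1 - Day 21) will be tabulated with exact 95% CI, overall and by MedDRA" class and term.

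**The concern.** A date with a known day and month but no year is not among the three flag-based patterns, so it takes the year of study entry. Entry and vaccination are both on Day 1 in the Schedule of Activities. If the 21-day window runs past 31 December, a January onset is placed in the January before vaccination, even when the eCRF says that the event followed the dose.

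The outcome is inconsistent with the SAP's own approach. If nothing is known about the date except that the event was post-dose, it is kept. If day and month are also known, it is lost. More information gives a worse answer, which suggests a drafting oversight.

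At stake is the primary unsolicited AE count and its sub-rows. The SAE count uses the same window and could be affected in the same way.

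**Working it through.** The documents give no figure for this rule, so there is none to reproduce. As a check on the interval method used in step 4, 25/250 gives Clopper-Pearson limits of 6.58% to 14.41%, which match SAP Table 2.

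**Inputs.** Window: Day 1 to Day 21, with Day 1 the vaccination date (SAP 4.1.2, 4.2.1). N=250 (SAP 1.2). Vaccination year 2023 is an assumption: the formulation is NH 2023-2024 and the trial runs in the Northern Hemisphere season (Protocol 5.1), but no enrolment dates are given.

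**1. Which vaccination dates are exposed.** Day 21 is 20 days after vaccination. It reaches 1 January only if vaccination is on or after 12 December (12 Dec + 20 days = 1 Jan). The exposed dates are therefore 12 to 31 December. For other dates the window stays in one calendar year, and the study-entry year is correct for a post-dose onset in the window.

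**2. What the rule does to them.** Let k be the number of days from vaccination to onset. Imputing 2023 instead of 2024 moves the date back 365 days, so the imputed offset is k − 365.

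- Vaccination 20 Dec 2023, onset 5 Jan, year unknown, flag *after study dose*: k = 16, so the true onset is Day 17. Imputed date: 5 Jan 2023. Offset: 16 − 365 = −349 days.
- January onsets inside the window have k from 1 to 20, so offsets run from 1 − 365 = −364 to 20 − 365 = −345 days.
- From 12 to 31 December the number of January days in the window rises from 1 to 20, giving 1 + 2 + … + 20 = 210 combinations of vaccination date and onset. All 210 land before the dose. If the year is instead chosen to agree with the flag, all 210 stay within Day 1–21.

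**3. Only the year known, and it is the year after vaccination.** The AE rule does not apply, because it requires the vaccination year. The standard rule for missing day and month covers only a prior year or the entry year. No date is assigned, and the SAP does not say whether an undated AE counts. An onset within Day 21 is again possible only after vaccination on 12–31 December.

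**4. Size per affected participant.** If the lost event was the participant's only qualifying AE, the count falls by 1/250 = 0.4 percentage points:

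| With the event (95% CI) | Without it (95% CI) |
|---|---|
| 1/250 (0.01–2.21%) | 0/250 (0–1.46%) |
| 3/250 (0.25–3.47%) | 2/250 (0.10–2.86%) |
| 25/250 (6.58–14.41%) | 24/250 (6.25–13.95%) |

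If the participant had another qualifying AE, the overall row does not change, though a class or term row may.

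**5. Whether another section repairs it.** SAP 4.1.3 lets eCRF information override timing only for events that start on the reference start date. No other section corrects an imputed AE date that precedes the dose.

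**The case against.** The strongest reply is that the rule will hardly ever be reached. It needs vaccination in the last 20 days of December, a January onset, and a recorded day and month without a year. Diaries are completed daily (Protocol 5.7), with a call at Day 8 (+2) and card review at Day 22 (+3). The eCRF has programmed checks for missing or illogical data, with queries (7.6), and source data are verified (7.5). SAEs are reported within 24 hours (5.5.1). With 22 days of participation, a known day and month leave only one plausible year for a post-dose event, so a query should settle it. All of this stands, and it makes the expected number of affected records small. It does not correct the rule. The SAP provides for incomplete dates that survive cleaning, and for this pattern the provision gives a wrong date.

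Three stronger readings are tempting, and the documents do not support them:

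- *That the effect can be sized from the share of participants whose window crosses the year end.* This needs enrolment dates, which are not given. It would also count all January onsets, not the few with an incomplete year, whose frequency is unknown.
- *That the fallback can only lower the AE count.* This is true of the flagged post-dose, year-missing case. The same sentence also sends a date with a missing day in a later month to the first of that month. Take vaccination on 20 November and true onset on 12 December: 22 days later, so Day 23. Recorded as December with no day, it becomes 1 December: 11 days later, so Day 12, and it is counted.
- *That an AE with only the following year known is excluded.* The SAP leaves it undated. Its place in the count is undefined, which is a gap but not a shown loss.

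**Conclusion.** The point holds as a minor error in a written rule. For unsolicited AE start dates with day and month known and year missing, SAP 6.2.3.2 overrides a post-dose flag. Any January onset within Day 21 of a 12–31 December vaccination is then placed 345 to 364 days before the dose and out of the primary count. The year-only pattern for the following year is a separate gap.

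The text reading and the date arithmetic are firm. That any participant is vaccinated on those dates is an assumption, plausible for the Northern Hemisphere 2023-2024 season but not stated. The number of such records is unknown and should be very low. Each costs at most 0.4 percentage points at N=250, and the trial is descriptive with no hypothesis test, so no conclusion is likely to turn on it. The case for changing it is that the correction is nearly free and makes the rule consistent with its own three named patterns.

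**What to change.** In SAP 6.2.3.2, replace the fallback sentence with:

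> For any other incomplete unsolicited AE start date, AE.AESTTPT is applied first. If it is 'after study dose', use the earliest date on or after vaccination (Day 1) consistent with the known date parts. If it is 'before study dose', use the latest date before vaccination consistent with the known parts. If the flag is missing, treat the event as 'after study dose' unless the known parts show that it started before vaccination.

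The last clause is needed because, without it, a record with a blank flag would have no rule. The wording dates the example to 5 January 2024 (Day 17). It also gives the year-only case a date, 1 January of the following year. A missing day in a later month still goes to the first of that month, so that pattern continues to err towards counting the event.

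The cost is one SAP sentence and a few lines of derivation code. No new data are needed, because the flag is already collected.
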